4.9.3 Secondary Efficacy Variables

4.9.3.1 UACR at 12 Weeks

Urine ACR will be analysed to determine the dose-response effect of AZD5718 at 12 weeks (on current standard of care). The population of interest are randomised participants who meet all eligibility criteria and have valid non-missing urine ACR records at baseline and at least one post-treatment visit. The mean log change from baseline in urine ACR will be analysed using a mixed model for repeated measures. The summary measure being evaluated is the geometric mean reduction of urine ACR from baseline to Week 12. This will be evaluated using the same methods for the primary efficacy endpoint. The analysis will be repeated on the Per-Protocol Analysis Population.

The results of the model parameters (estimates, p-values, and 95% CIs) will be presented. The point estimate and 95% CI for the geometric mean ratio will be converted to the percentage change as follows:

$$[(\text{Geometric Mean Ratio} - 1) \times 100]$$

UACR will be summarized by treatment group and visit in terms of absolute values and changes from baseline.

The analysis will be repeated by strata (DKD without SGLT2i background, DKD with SGLT2i background, non-DKD), with the analysis model will include the fixed categorical effects of treatment, visit, and treatment-by-visit interaction, plus the continuous covariates of baseline log (urine ACR) and baseline log (urine ACR)-by-visit interaction.

4.9.3.2 Estimated GFR

Estimated GFR will be analysed, comparing eGFR at baseline with that at 12 weeks, to determine whether there is any acute change with the introduction of AZD5718 to inform planning for a GFR slope analysis in Phase 3. This will be analysed using a by-visit ANCOVA, adjusting for DM stratification factor, treatment group and baseline eGFR. The FAS will be used for this analysis and eGFR will be evaluated on the original scale. The analysis will be repeated on the Per-Protocol Analysis Population.

The results of the by-visit ANCOVA will be presented by treatment group. A summary of change from baseline of eGFR results will be presented by treatment group and a by-participant listing provided of eGFR results at each visit. Plots of the least-squares mean by treatment group over time, and the mean eGFR over time up to follow-up visit will be presented.

An ANCOVA model will be produced for eGFR up to Week 20, analysed on the Per-Protocol Analysis set, similarly to that described above.

The analysis will also be repeated by strata (DKD without SGLT2i background, DKD with SGLT2i background, non-DKD), adjusting for treatment group and baseline eGFR.

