7 DISCONTINUATION OF STUDY INTERVENTION AND PARTICIPANT DISCONTINUATION/WITHDRAWAL

7.1 Discontinuation of Study Drugs

Participants are free to discontinue study drugs at any time, without prejudice to further treatment.

- Participants who choose to discontinue AZD5718 prior to the end of Treatment Period 1 will not proceed to Treatment Period 2 and are expected to complete the assessments per Discontinuation Visit and Follow-up Visit.
- Participants who choose to discontinue either AZD5718 or dapagliflozin prior to the end of Treatment Period 2 are expected to continue in the study on the remaining study therapy and are expected to complete the study assessments according to the schedule of study procedures for the remainder of the study.
- Participants who choose to discontinue both AZD5718 and dapagliflozin prior to the end of Treatment Period 2 are expected to complete the study assessments according to the schedule of study procedures for the remainder of the study.

See the SoA ([Table 1](#)) for data to be collected at the time of discontinuation of study drugs and follow-up and for any further evaluations that need to be completed.

The Investigator and/or Study Physician may determine that an individual participant will not receive any further study drug if any of the following occur in that participant:

- Withdrawal of consent from further treatment with study drugs.
- Lost to follow-up.
- Safety reasons as judged by the Investigator and/or Sponsor where continued treatment may put the participant at undue risk.
- Incorrectly randomised participant in whom inclusion/exclusion criteria violation would put the participant at undue risk.
- Participant noncompliance that, in the opinion of the Investigator or Sponsor, warrants treatment discontinuation for safety reasons (eg, refusal or inability to adhere to scheduled visits).
- Pregnancy.
- Any of the following liver function abnormalities:
 - ALT or AST $> 8 \times$ ULN
 - ALT or AST $> 5 \times$ ULN for more than 2 weeks
 - ALT or AST $> 3 \times$ ULN and (total bilirubin $> 2 \times$ ULN or international normalised ratio [INR] > 1.5); see [Appendix E](#) for additional details regarding reporting of participants with ALT or AST $\geq 3 \times$ ULN and total bilirubin $\geq 2 \times$ ULN with unknown aetiology (ie, Hy's Law [HL] cases)

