 - ALT or AST $> 3 \times$ ULN with the appearance of fatigue, nausea, vomiting, right upper quadrant pain or tenderness, fever, rash, and/or eosinophilia ($> 5\%$)

If an unexpected, acute decline in GFR is observed ($> 15\%$ decrease in eGFR from the

Screening Visit values), the participant should be promptly evaluated. Volume depletion, hypotension, inter-current medical problems, and concomitant drugs may cause increases in blood creatinine. Urinary tract infection and urinary obstruction should be considered. Several drugs may cause a decline in GFR, especially NSAIDs and certain antibiotics such as trimethoprim. If any drug is suspected of causing or contributing to worsening kidney function, their use should be re-considered. The Investigator together with the Study Physician should consider the discontinuation of the investigational medicinal product (IMP) if eGFR decreases by more than 30% of Screening Visit values.

Consider temporary interruption of dapagliflozin if DKA is suspected. The participant should be promptly evaluated. If DKA is confirmed, dapagliflozin should be discontinued permanently.

Note that discontinuation from study drugs is NOT the same thing as a withdrawal from the study.

Participants who are permanently discontinued from receiving the study drugs will be followed for protocol-specified assessments, including follow-up of any AEs, unless consent is withdrawn specifically from further study participation (Section 7.2), the participant is lost to follow-up (Section 7.2), or the participant is enrolled in another clinical study.

A participant who decides and/or is recommended by the treating physician or the Investigator to permanently discontinue the study drugs will always be asked about the reason(s) for discontinuation and about the presence of any AEs. All efforts must be taken to ensure that the participant will be seen and assessed by an Investigator and, as scheduled for other participants, all end of treatment visit assessments should be completed at the time of discontinuation of study drug.

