4.14 Changes in the Conduct of the Study or Planned Analysis

Following the results from the interim analysis, it was decided to terminate the study early and reduce the scope of analysis. This decision led to the removal of the MCP-Mod analysis as outlined in the protocol, and the previously described sensitivity analysis for the ABPM analysis. The statistical analysis plan has been updated to include only the analysis which will be performed following database lock.

Pharmacokinetic analyses of AZD5718 and dapagliflozin were also removed from the final analysis. The statistical analysis plan has been updated to reflect this.

Due to the early termination of the study, the total number of randomised participants is 613 with 340 participants completing treatment. Therefore, efficacy analyses should be evaluated with caution due to lack of power.

The total study duration, as highlighted in Section 3.1, will vary following study termination, up to a maximum of 28 weeks.

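### The Week 12 eGFR contrast comes from a by-visit ANCOVA with no missing-data rule, so it can understate an acute fall if eGFR-driven stopping removes Week 12 values, and it loses some precision in any case

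*SAP*

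**What the plan says.** SAP 4.9.3.2 (and Protocol 9.4.2.2) compares eGFR at baseline with eGFR at Week 12. The aim is "to determine whether there is any acute change with the introduction of AZD5718 to inform planning for a GFR slope analysis in Phase 3". On method it says "This will be analysed using a by-visit ANCOVA, adjusting for DM stratification factor, treatment group and baseline eGFR", and on the analysis set "The FAS will be used for this analysis and eGFR will be evaluated on the original scale". The analysis is repeated on the Per-Protocol population, and an ANCOVA up to Week 20 is run on that set. Earlier visits are also reported: "Plots of the least-squares mean by treatment group over time" are planned.

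SAP 4.9.1.4 leaves missing UACR unimputed and generally leaves safety data unimputed. It has no rule for eGFR. Week 12 UACR, by contrast, gets an MMRM (SAP 4.9.3.1, using the methods of 4.9.2.1).

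Protocol 7.1 has two eGFR triggers. At a fall above 15%, "the participant should be promptly evaluated". At a larger fall, the investigator with the Study Physician "should consider the discontinuation of the investigational medicinal product (IMP) if eGFR decreases by more than 30% of Screening Visit values". Participants who choose to stop AZD5718 in Treatment Period 1 "will not proceed to Treatment Period 2 and are expected to complete the assessments per Discontinuation Visit and Follow-up Visit". Later in the same section, participants permanently off study drug are said to stay under follow-up for the assessments that the protocol schedules.

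SAP Table 2 maps visits by actual assessment day. Week 12 is D72 to D88, and the Discontinuation Visit is left out of the mapping. SAP 4.14 reports that "the total number of randomised participants is 613 with 340 participants completing treatment".

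**The concern.** A by-visit ANCOVA gives a participant no weight in the Week 12 contrast unless a Week 12 value exists. It is unbiased for the full randomised comparison only if being missing at Week 12 is unrelated to Week 12 eGFR, given arm, baseline and stratum. Protocol 7.1 opens a route by which that can fail: a large observed fall may lead to stopping, and stopping in Period 1 may mean no Week 12 visit. The eGFR taken at stopping is then lost as well, because Discontinuation Visit values map to no analysis visit.

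The Per-Protocol repeat does not test this. That population requires dapagliflozin after Week 12, so anyone who stopped in Period 1 is outside it by definition.

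At stake is the Week 12 estimate of an acute renal effect, which is a secondary endpoint. The method is least dependable in the situation it is meant to detect.

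**Working it through.** **Design figures.** The documents give no sample size, SD, effect or missing-data rate for eGFR, so there is no planned eGFR figure to reproduce. The UACR design implies an overall loss of 1 − 142/158 = 10.1%. After termination, 613 − 340 = 273 did not complete treatment, and 273/613 = 44.5%. This is an upper bound on Week 12 loss through non-completion, since some of the 273 stopped after Week 12.

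**Bias: simulation set-up.** One dose against placebo, 158 per arm, Weeks 2, 4, 8 and 12, 400 to 800 replicates. These inputs are assumptions, not figures from the documents:
- baseline eGFR mean 43, SD 14, clipped to the 20–75 eligibility range;
- measurement CV 8%, and drift SD 10% by Week 12;
- a drug effect constant from Week 2;
- a fall above 30% from simulated baseline at Weeks 2, 4 or 8 leads to stopping with probability 0.5 or 1.0, with no later eGFR, and the triggering value stays in the data.

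Understatement = 1 − (ANCOVA estimate / complete-data estimate). Week 12 differences are in mL/min/1.73 m².

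| Drug effect (fall) | Stop prob. | Stopped: placebo / active | Complete data | ANCOVA | MMRM | ANCOVA understates by |
|---|---|---|---|---|---|---|
| None | 1.0 | 1.1% / 1.1% | +0.03 | +0.03 | +0.03 | none |
| Uniform 5% | 0.5 | 0.6% / 1.5% | −2.10 | −2.02 | −2.10 | 4% |
| Uniform 5% | 1.0 | 1.1% / 3.0% | −2.15 | −1.99 | −2.14 | 8% |
| Uniform 10% | 0.5 | 0.5% / 3.6% | −4.14 | −3.92 | −4.14 | 5% |
| Uniform 10% | 1.0 | 1.1% / 6.5% | −4.16 | −3.76 | −4.14 | 10% |
| Mean 5%, SD 10% | 0.5 | 0.6% / 4.0% | −1.93 | −1.55 | −1.90 | 20% |
| Mean 5%, SD 10% | 1.0 | 1.1% / 7.0% | −1.96 | −1.29 | −1.88 | 34% |
| Mean 10%, SD 10% | 0.5 | 0.6% / 7.3% | −3.88 | −3.22 | −3.83 | 17% |
| Mean 10%, SD 10% | 1.0 | 1.0% / 12.1% | −3.92 | −2.82 | −3.79 | 28% |

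SD 10% means that the drug effect varies between participants. A deliberately extreme case (mean 10%, SD 15%, stop probability 1.0) gave −3.71 / −1.74 / −3.47, an understatement of 53%. The Week 2 by-visit estimate was essentially unbiased: −3.93 in the mean 10%, SD 10%, stop probability 1.0 scenario, where the complete-data Week 12 value is −3.92.

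**What the MMRM needs.** Its near-full recovery depends on the triggering value being in the model. A second simulation (baseline 45, SD of change 6, between-visit correlation 0.7, true effect −3.0) recorded that value only at the unmapped Discontinuation Visit. ANCOVA then gave −2.68 and the MMRM −2.80 at 50% stopping, and −2.51 against −2.61 at 100%. Most of the bias remained.

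**Precision.** With random truncation and no eGFR-driven stopping, the SE ratios (ANCOVA / MMRM) are:
- 10% missing: 0.896 / 0.870 = 1.03
- 25% missing: 0.982 / 0.939 = 1.05
- 45% missing: 1.150 / 1.025 = 1.12

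**Follow-up values.** If the Follow-up Visit comes 28 days after stopping (assumed from Day 141 to Day 169), stopping on Day 72 − 28 = 44 to Day 88 − 28 = 60 would place it on D72 to D88. Table 2 would then count an off-drug value as Week 12.

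**The case against.** The strongest case against is that the link from a large fall to a missing Week 12 value is not written down. The protocol asks only that stopping be considered above 30%. The two-visit rule covers participants who choose to stop, and later text in 7.1 keeps permanently discontinued participants under scheduled assessments. If that text governs, much of the missingness disappears. This stands, and it is why the claim must be conditional.

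The size is also open to challenge. At stopping probabilities of 10% to 25%, the second simulation reads a true −3.0 as −2.92 to −2.73, an understatement of 3% to 9%. In the main table the uniform-effect bias is 0.08 to 0.40 mL/min/1.73 m², well inside a standard error of 0.7 or more. With varying response it is 0.38 to 1.10, against standard errors of about 0.8 to 0.9. That is not negligible, but it rests on assumed variation.

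A reader might infer that earlier eGFR data are wasted. They are not: each visit has its own estimate and is plotted, and an acute effect would show at Week 2. They are unused only for the Week 12 contrast. A reader might also infer that termination biases the result. SAP 4.12.1 gives lack of efficacy as the reason and reports no safety concern, so that truncation is administrative and costs precision.

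The Phase 3 purpose has weakened since termination, and the ANCOVA is the protocol-specified method. Both points favour adding an MMRM beside it rather than replacing it.

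**Conclusion.** The point holds in conditional form. Understatement at Week 12 requires three things together: a real eGFR-lowering effect, more eGFR-driven stopping on active drug than on placebo, and absent Week 12 values. Given all three, plausible sizes run from about 4% to about a third. With no drug effect there is no bias. The documents do not support saying that the contrast is understated, because they give no stopping rate and conflict on post-stopping assessments. Observed-only analysis is itself the default reading of a silent SAP, not a stated rule.

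The precision loss needs none of those conditions. It is roughly 3% to 12% in standard error for 10% to 45% missing, with 44.5% as the ceiling from non-completion. The MMRM also needs a weaker missingness assumption, since it conditions on earlier eGFR as well as on arm, stratum and baseline.

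**What to change.** In SAP 4.9.3.2:

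1. Add an MMRM for change in eGFR with stratification factor, treatment, visit, treatment-by-visit, baseline eGFR and baseline eGFR-by-visit, unstructured covariance and Kenward-Roger degrees of freedom. Use Weeks 2, 4, 8 and 12 on the Full Analysis Set, and visits through Week 20 on the Per-Protocol set.
2. Report its Week 12 contrast alongside the by-visit ANCOVA, and record the addition in 4.14.
3. For this model, map Discontinuation Visit eGFR to the nearest analysis visit so that the triggering value is kept. State whether early termination visits are handled the same way.
4. Do not let an off-drug Follow-up value on D72 to D88 count as on-treatment Week 12.
5. State that missing eGFR is not imputed and that the MMRM assumes missing at random.

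Separately, the two statements in Protocol 7.1 on assessments after stopping must be reconciled, and the SAP should say which data it expects as a result.

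The cost is one model adapted from the UACR code, a stated missing-at-random assumption, and a departure from the protocol-specified analysis made after an unblinded interim review. SAP 4.12.1 says the main study team stayed blinded. No sample size changes.

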4.9.3.3 Ambulatory Blood Pressure Monitoring

For drugs intended for chronic use, the US Food and Drug Administration (FDA) recommended use of ambulatory blood pressure monitoring (ABPM) to assess the sustained BP effect ([FDA guidance on Assessment of Pressor Effects of Drugs, May 2018](#)). The collection and the analysis of the ABPM data in this study is aimed to delineate differential BP effect of AZD5718 relative to placebo.

The device will be provided to the participants at the visits outlined in the SoA in [Appendix A](#) (Screening Visit 2 and Visit 6 [Week 8]). They will be instructed to perform the ABPM 24-hours before their next visit, ie, Visit 3 (Week 1) and Visit 7 (Week 12), respectively. The ABPM recording must have finished prior to dosing at each specified visit.

If the 24-hour ABPM assessment session provided at a visit is confirmed to not meet the validity criteria, the associated study visit may be rescheduled to allow for a repeat ABPM recording only if the rescheduled visit can be completed within the specified tolerance period for study visits, as described in the SoA in [Appendix A](#). An assessment session is valid if there is a minimum of 20 hours of the recording with at least 70% of expected measurements being successful. If the repeated assessment session is not valid using the same validity criteria, no further repeats will be performed for that visit. This criterium for the validity of measurements will only be used on site to reschedule the ABPM assessment session. The inclusion criteria for the statistical analysis are separate and are described in the following paragraph.

Recordings will be done every 20 minutes during the day-time (06:01 to 22:00) and every 30 minutes during the night-time (22:01 to 06:00). These definitions of day-time and night-time are only to be used on site for collecting recordings; they will be defined differently for the purpose of statistical analyses.

For the purpose of inclusion in the statistical analyses, the session needs to satisfy two conditions:

1. There should be at least 50% of successful measurements in both day-time (06:01 to 22:00) and night-time (22:01 to 06:00). If both the scheduled and repeat assessment sessions have more than 50% of successful measurements in the respective timeframes, the assessment session with a higher overall percentage of successful measurements will be included in the analyses. In the unlikely event that both the scheduled and repeated assessment sessions have the same percentage of successful measurements (and both above 50%), the scheduled assessment session will be taken as the visit assessment.
2. There are not more than two consecutive hours with no available measurements in an ABPM assessment session.

Primary ABPM Analysis

The primary endpoint in the analysis is the change from baseline in 24-hour mean SBP at Week 12. Participants with missing mean 24-hour SBP at Week 12 will be excluded from the analysis.

In order to derive the mean SBP over various time periods, the hourly mean SBP is derived for each participant for each hour using the available data at the visit. This is the sum of the successful non-missing SBP measurements in the hour, divided by the number of non-missing SBP measurements in the respective hour. This derivation will be used to further derive the endpoints of interest.

The 24-hour mean SBP is derived as the sum of the non-missing hourly mean SBP measurements, divided by the number of hours with non-missing hourly mean SBP. Missing hourly mean SBP derivations will not be counted towards the 24-hour mean.

For the ABPM analysis, baseline for the 24-hour mean ABPM parameter (or mean day-time, mean night-time, mean hourly) is defined as the 24-hour mean value (or corresponding mean day-time value, mean night-time value, mean hourly value) during the Screening Visit 2.

The change from baseline in 24-hour mean SBP at Week 12 will be analysed using an ANCOVA model, with change from baseline in 24-hour mean SBP as the dependent variable, adjusting for DM stratification factor, treatment group (AZD5718 **CC** mg, AZD5718 **CC** mg, AZD5718 **CC** mg, placebo), plus baseline 24-hour mean SBP and BMI as covariates. The ambulatory blood pressure monitoring population will be used for this analysis. The least squares (LS) mean difference between each of the AZD5718 doses and placebo (ie, placebo-corrected change from baseline in 24-hour mean SBP) will be derived from the model. The 2-sided 90% CI for these differences will be presented.

If the proportion of participants within a sub-group category is too small for effective analyses, sub-group categories can be collapsed or removed from the sub-group analyses, where appropriate.

The change from baseline in 24-hour mean DBP at Week 12 will be analysed similarly to the primary endpoint using an ANCOVA model. The 2-sided 90% CI for the difference between each of the AZD5718 doses and placebo will be derived from the model and presented.

Sensitivity ABPM Analysis – 24-hour Mean SBP

The proportion of missingness of ABPM data (the number of participants who did not meet either of the statistical validity criteria at baseline and Week 12) will be summarised by treatment group and by key baseline characteristics (age group, race, BMI group, and randomisation strata).

Secondary ABPM Analysis

The secondary ABPM endpoints are change from baseline in mean day-time and mean night-time ABPM metrics (SBP and DBP), these will be evaluated similarly to the primary ABPM endpoint using ANCOVA models, presenting only the 90% CI between each of the AZD5718 doses and placebo. No formal hypothesis testing will be performed. Day-time is defined as 09:00 to 21:00, night-time is defined as 01:00 to 06:00.

The mean day-time SBP will be derived as the sum of the hourly mean SBP from 09:00 to 21:00 divided by the total number of hours with non-missing data. The mean night-time SBP will be derived as the sum of the hourly mean SBP from 01:00 to 06:00 divided by the total number of hours with non-missing data. The same derivations will be performed for DBP. Summary statistics will be presented for mean day-time and night-time values.

By-participant listing for ambulatory blood pressure monitoring values and derivations will be presented by treatment group and visit.

4.10 Safety Evaluation

All safety summaries and analyses will be based upon the Safety analysis set as defined in Section 4.5, unless otherwise specified. Safety summaries will be presented by treatment group and with a pooled AZD5718 group, where appropriate.

Change from baseline will be calculated as the differences between the post-dose value at each time point and the value prior to administration of the study medication.

Individual safety and tolerability data will be provided in data listings and summarised as appropriate by treatment and overall. Continuous variables (laboratory parameters, ECG, and blood pressure) will be summarised using descriptive statistics (n, mean, SD, minimum, median, and maximum) as appropriate by scheduled assessment time point. Where applicable, data will be summarised for the observed value, and for the corresponding change from baseline/screening. Categorical variables will be summarised in frequency tables (counts and percentage) as appropriate by scheduled assessment time point too.

Outputs presented on the Extended Safety Analysis Set will include the Week 12 flag to subset for data in the second treatment period. These outputs may be repeated without the Week 12 flag if deemed appropriate by the study team, thereby including all data for participants who continued into the second treatment period only.

